6.1.7 MyCareLink[®] Home Monitor

The MyCareLink[®] Home Monitor is a device that enables the device diagnostic data (which includes ECG data) to be transmitted directly from the implanted Reveal LINQ[™] device to the Medtronic CareLink[®] Network for review by the physician.

Medtronic Business Restricted

21 SEP 2022

Version 2

Figure 5: MyCareLink[®] Patient Monitor

6.1.8 DR 220 Holter Monitor

The NorthEast Monitoring, Inc. DR220 Digital Recorder is a Holter monitor that is commercially available and designed to facilitate the ambulatory cardiac monitoring of those subjects who may benefit from such monitoring on the order of a physician, including but not limited to those with complaints of palpitations, syncope, chest pains, shortness of breath, or those who need to be monitored to judge their current cardiac function, such as subjects who have recently received pacemakers. The DR220 Digital Recorder is intended for use with Medtronic System-B compatible implantable pulse generators, implantable cardiac defibrillators, cardiac resynchronization therapy devices and implantable cardiac monitors. A Holter monitor is an external box used to record electrical heart signals from electrode patches attached to the skin (ECG) as well as from the cardiac device (EGM). There are no contraindications for the use of a DR220 Holter monitor. The Holter monitor will be used in accordance with its labeling. Only trained study personnel should apply the monitors.

The data obtained by monitoring is not analyzed at the time of recording. After the recording is complete, the data must later be downloaded to a compatible NorthEast Monitoring, Inc. Holter analysis system to be analyzed. No personal information will be entered and collected by DR220 recorder.

The DR220 Holter Recorder used in this study is a portable ECG device able to collect telemetry signals and marker channel information from any Medtronic device for up to 48 hours. The Holter Recorder has application for any subject with a Medtronic ICM. For the purposes of this study, the intended use of the Holter Recorder is to collect LINQ[™] ECG recordings in order to measure QT intervals.

Medtronic Business Restricted

Page 18 of 48

21 SEP 2022

Version 2

Figure 6: DR220 Holter

6.2 Shipment of Study Components

Medtronic will only allow shipment of the study device and components to the hospital or investigator when Medtronic has received all required documentation and has notified the site of readiness. Products shall be used in these centers only and according to the CIP. Clinical that are used for purposes of the study only will be provided at no cost by Medtronic. Distribution of the study device and components to centers during the study will be managed by Medtronic.

6.3 Product Accountability

Commercially available product supply will be managed in a manner consistent with other marketreleased products.

All products used in this study will be market released in the geographies they are used. Device Traceability may be required per local laws and regulations. If there are additional local requirements related to the LINQ QT study components beyond what is collected by Medtronic on the eCRF, this is the Investigator's responsibility and should be recorded in the subject's medical records, but will not be collected by Medtronic (e.g., national registration card number, identification code linked to names and contact information, log of all subjects enrolled in the study, lot, or batch number).

Medtronic Business Restricted

21 SEP 2022

Version 2

Page 19 of 48

7. Selection of Subjects

7.1 Study Population

The subject population for the LINQ QT Study are patients implanted with LINQ[™]/LINQII[™] prior to the study enrollment (no more than 50% patients implanted with LINQII[™]), but no greater than 2 years for LINQ[™] or 3 years for LINQII[™], or patients who are indicated to receive a LINQ[™]/LINQII[™] implant at least 7 days prior to antiarrhythmic drug loading and who are scheduled to receive an antiarrhythmic drug loading, may undergo this study.

7.2 Subject Enrollment

Ethics Board/IRB and Medtronic approval of this Clinical Investigation Plan, the informed consent form and any other applicable documents must be obtained prior to enrolling subjects in the study. Medtronic will provide each study center with documentation of study center/investigator readiness; this letter must be received prior to subject enrollment.

When a patient and the principal investigator or authorized designee, as required, have personally signed and dated the informed consent form, the patient is considered a subject enrolled in the study. Subjects must provide informed consent before any study related procedures occur. The date the subject signed the informed consent form and data protection authorization as required by local law must be documented in the subject's medical records.

7.3 Inclusion Criteria

- Patients implanted with LINQ[™]/LINQII[™] prior to the study enrollment (no more than 50% patients implanted with LINQII[™]), but no greater than 2 years for LINQ[™] or 3 years for LINQII[™], or patients who are indicated to receive a LINQ[™]/LINQII[™] implant at least 7 days prior to antiarrhythmic drug loading
- Patients who are scheduled to receive antiarrhythmic drug loading
- Up to 20% of patients enrolled in the study can have permanent and persistent AF
- Age 18-80
- Patient is willing and able to comply with the protocol, including follow-up visits, and performing Holter recordings and patient activation transmissions

7.4 Exclusion Criteria

- Patients who have a contraindication to long-term antiarrhythmic therapy
- Patients not suitable for long-term antiarrhythmic therapy
- Patients with a previous, existing cardiac implantation (i.e., cardiac pacemaker or cardiac resynchronization requiring > 40% pacing, implantable cardioverter defibrillator (ICDs))
- Co-enrollment in another study or planning to participate in a concurrent device study during the course of this clinical study that could confound the results

Medtronic Business Restricted

21 SEP 2022

Version 2

Page 20 of 48

8. Study Procedures

8.1 Schedule of Events

A patient will be considered enrolled in the study once they sign and date the Informed Consent. The subjects will be followed at in-office visits during study participation. In addition, the subjects will be completing daily manual device transmissions. The requirements for data collection and study procedures by visit are summarized in Table 2 below.

8.2 Data Collection

Data collection requirements are summarized in Table 2 below.

Medtronic Business Restricted

LINQ QT Study Clinical Investigation Plan			
21 SEP 2022	Version 2	Page 21 of 48	Medtronic

Table 2: Data collection and study procedure requirements at subject visits

Medtronic Business Restricted

LINQ QT Study Clinical Investigation Plan Medtronic 21 SEP 2022 Version 2 Page 22 of 48

8.3 Subject Screening

Subjects will be screened to ensure they meet all the inclusion criteria and none of the exclusion criteria prior to study enrollment. The subject will be considered enrolled after both the subject and the investigator (or authorized designee as required by the informed consent form [ICF]) have each personally signed and dated the ICF.

8.4 Subject Consent

The ICF is defined as a legally effective documented confirmation of a subject's voluntary agreement to participate in a particular clinical study after information has been given to the subject on all aspects of the clinical study that are relevant to the subject's decision to participate. This process includes obtaining an ICF and an Authorization to Use and Disclose Personal Health Information/Research Authorization/other privacy language as required by law that has been approved by the study site's Institutional Review Board/Ethics Committee (IRB/EC) and signed and dated by the subject.

Investigators shall consider all subjects who meet eligibility requirements for study participation to avoid any bias in the subject population. Prior to enrolling subjects, approval of the CIP, ICF, and any other written study information to be provided to the subjects must have been obtained from each site's IRB/EC. The document(s) must be controlled (i.e., versioned and dated) to ensure it is clear which version(s) were approved by the IRB/EC. Any adaptation of the sample ICF must be reviewed and approved by Medtronic and the IRB/EC reviewing the application prior to enrolling the subject.

The investigator must notify the subject of any significant new findings about the study that become available during the study which are pertinent to the safety and well-being of the subject, as this could impact a subject's willingness to participate in the study. If relevant, approval may be requested from subjects to confirm their continued participation.

The informed consent form template will be sent under a separate cover.

Prior to initiation of any study-specific procedures, informed consent must be obtained from the subject. Likewise, privacy or health information protection regulation may require subjects to sign additional forms to authorize sites to submit subject information to the study sponsor. The informed consent process must be conducted by the principal investigator or his/her authorized designee, and the ICF and Authorization to Use and Disclose Personal Health Information/Research Authorization/other privacy language as required by law must be given to the subject in a language, he/she is able to read and understand. The process of obtaining informed consent must be conducted without using coercion or undue improper influence on or inducement of the subject to participate by the investigator or other site personnel. The informed consent process shall not waive or appear to waive subject's legal rights. The language used shall be as non-technical as possible and must be understandable to the subject and the impartial witness, where applicable.

Medtronic Business Restricted

LINQ QT Study Cl	inical Investigation	Plan	
21 SEP 2022	Version 2	Page 23 of 48	Medtronic

The subject must have ample time and opportunity to read and understand the ICF, to inquire about details of the study, and to decide whether to participate in the clinical study. All questions about the study should be answered to the satisfaction of the subject.

When the subject decides to participate in the clinical study, the ICF must be signed and personally dated by the subject acknowledging that their participation is voluntary and signed and personally dated by the investigator or authorized designee as required by the ICF. If applicable, the witness shall also sign and personally date the ICF to attest that the information in the ICF was accurately explained and clearly understood by the subject, and that informed consent was freely given.

A copy of the ICF and the Authorization to Use and Disclose Personal Health Information/Research Authorization/other privacy language, signed and dated as required by law, must be provided to the subject.

If informed consent is obtained the same day the subject begins participating in study-related procedures, it must be documented in the subject's case history that consent was obtained prior to participation in any study-related procedures. It is best practice for the informed consent process to be documented in the subject's case history, regardless of circumstance.

In the event the subject cannot read and/or write, a witnessed (impartial third party) informed consent will be allowed. In this situation, an independent witness must be present throughout the informed consent process. The written informed consent form and any other information shall be read aloud and explained to the prospective subject. The subject should "make his/her mark" (sign or otherwise physically mark the document so as to indicate consent) on the ICF as well. The witness must also sign and personally date the ICF attesting that the information was accurately explained, and that informed consent was freely given. Detailed documentation of the consent process must be recorded in the subject's case history. The ICF should document a supervised oral process was used for communication with the prospective subject and the specific means by which the prospective subject communicated agreement to participate in the study.

The ICF and Authorization to Use and Disclose Personal Health information/Research Authorization/other privacy language as required by law must be available for monitoring and auditing. Any Medtronic Field personnel who support the Reveal LINQ[™]/LINQII[™] ICM insertion procedure must be able to review the subject's original signed and dated ICF and verify its completeness prior to proceeding with the insertion. In the event the Medtronic Field personnel identify informed consent as being incomplete, the study procedure will not be allowed to occur until the consent of the subject can be adequately and appropriately obtained.

8.5 Enrollment

A subject is considered enrolled when the consent process has been finalized. The date the subject (or the subject's authorized/designated representative or guardian) signed the IC and Data Protection

Medtronic Business Restricted

LINQ QT Study Cl	inical Investigation	Plan	
21 SEP 2022	Version 2	Page 24 of 48	Medtronic

Authorization, as required by law, must be documented in the subject's medical records. Enrollment can occur no greater than 2 years after a LINQ[™] implant, or no greater than 3 years for LINQII[™]. Subjects can also be enrolled who will be receiving a LINQ[™]/LINQII[™] implant at least 7 days prior to anti-arrhythmic drug loading.

8.6 Baseline

8.7 Index Antiarrhythmic Loading Event

1. Subjects with LINQ[™] Implants

Medtronic Business Restricted

LINQ QT Study Clinical Investigation Plan		Plan	
21 SEP 2022	Version 2	Page 25 of 48	Medtronic

2. Subjects with LINQII[™] Implants

8.8 Follow-up Visits

1. Subjects with LINQ[™] Implants

Medtronic Business Restricted

LINQ QT Study Clinical Investigation Plan			
21 SEP 2022	Version 2	Page 26 of 48	Medtronic

2. Subjects with LINQII[™] Implants

NOTE: Subjects may be compensated for completing the required daily activations.

8.9 Nightly CareLink Data Transmissions

Medtronic Business Restricted

21 SEP 2022

Version 2

Page 27 of 48

8.10 Recording Data

8.11 Deviation Handling

A study deviation is defined as an event within a study that did not occur according to the Clinical Investigation Plan or the Clinical Trial Agreement. If an infringement remains unresolved, multiple deviations need not be completed.

Prior approval by Medtronic is expected in situations where the investigator anticipates, contemplates, or makes a conscious decision to deviate. Prior approval is not required when a deviation is necessary to protect the safety, right or well-being of a subject in an emergency or in unforeseen situations beyond the investigator's control (e.g., subject failure to attend scheduled follow-up visits, inadvertent loss of data due to computer malfunction, inability to perform required procedures due to subject illness).

For medically justifiable conditions which preempt a subject's ability to complete a study-required procedure, it may be permitted to report only one deviation which will apply to all visits going forward. This may also apply for other unforeseen situations (e.g., the subject permanently refuses to complete a study required procedure and the data will not contribute to the primary end point analysis). However, prior approval from Medtronic is required for such situations.

All study deviations must be reported on the study deviation e-CRF regardless of whether medically justifiable, pre-approved by Medtronic, an inadvertent occurrence, or taken to protect the subject in an emergency. The deviation description and reason for deviation must be recorded. Multiple deviations of the same type at the same visit may be reported on one e-CRF.

In the event the deviation involves a failure to obtain a subject's consent or is made to protect the life or physical well-being of a subject in an emergency, the deviation must be reported to the IRB/EC as well as Medtronic within five (5) working days. Reporting of all other study deviations must comply with IRB/EC

Medtronic Business Restricted

LINQ QT Study Clinical Investigation Plan			
21 SEP 2022	Version 2	Page 28 of 48	Medtronic

policies and/or local laws and/or regulatory agency requirements and must be reported to Medtronic as soon as possible upon the center becoming aware of the deviation. Refer to Table 12 for geography specific deviation reporting requirements and timeframes for reporting to Medtronic and/or regulatory bodies.

Medtronic is responsible for analyzing deviations, assessing their significance, and identifying any additional corrective and/or preventive actions (e.g., amend the Clinical Investigation Plan, conduct additional training, terminate the investigation). Repetitive or serious investigator compliance issues may result in initiation of a corrective action plan with the investigator and site, and in some cases, necessitate suspending enrollment until the problem is resolved or ultimately terminating the investigator's participation in the study. Medtronic will provide site-specific reports to investigators summarizing information on deviations that occurred at the investigational site on a periodic basis.

8.12 Subject Exit, Withdrawal or Discontinuation

Study exit is defined as the moment when a subject officially stops participating in the study. Subjects will be considered exited upon completion of the study exit e-CRF. Prior to exiting a subject from the study, it is recommended to follow the subject until any ongoing AEs are resolved/unresolved with no further actions planned, or until official study closure, whichever occurs first. The date and reason for subject exit must be reported to Medtronic at the earliest opportunity via eCRF. Exited subjects will not be replaced. Upon exiting from the study, no further study data will be collected, or study visits will occur for the subject. All data available through the time of the subject's exit will be used for analysis. Subjects are urged to remain in the study as long as possible but may be exited from the study for any of the following situations:

- Subject did not meet inclusion/exclusion criteria
- LINQ[™]/LINQII[™] ICM explanted and not replaced with a new LINQ[™]/LINQII[™] ICM (e.g., diagnosis determined, suspected infection, subject request, physician determination)
- Subject chooses to withdraw (e.g., consent withdrawal, relocation to another geographic location)
- Investigator chooses to withdraw a subject (e.g., medically justified, inclusion/exclusion criteria not met, failure of subject to maintain adequate study compliance)
- Subject lost to follow-up
- Death
- Study completion or termination

The following information/procedure is to be collected/performed at study exit:

- Date of exit
- Reason for exit

Medtronic Business Restricted

LINQ QT Study Cli	nical Investigation	Plan	
21 SEP 2022	Version 2	Page 29 of 48	Medtronic

In the case that the subject is determined to be lost to follow-up, details of a minimum of two attempts and the method of attempt (e.g., one letter and one phone record or two letters) to contact the subject must be recorded. In addition, follow the regulations set forth by the governing IRB/EC.

9. Risks and Benefits

9.1 Potential Risks

There are no incremental risks introduced to the subject as a result of participation in this study.

9.2 Risk Minimization

Any potential risks associated with this study are further minimized by selecting qualified investigators and training study personnel on the CIP.

9.3 Potential Benefits

The LINQ QT Study may offer no direct personal benefit to individual subjects.

Medtronic Business Restricted

21 SEP 2022

Version 2

Page 30 of 48

10. Adverse Events and Complaint Reporting

All products used are approved, not investigational and the purpose of the LINQ QT study is not to demonstrate safety or effectiveness. Cardiovascular-related or serious adverse events that result in a hospitalization due to anti-arrhythmic loading will be collected throughout out the duration of the subject's participation in the study, beginning after the initial in-hospital/out-patient anti-arrhythmic loading. Deaths will not be collected unless it resulted in a CV-related hospitalization related to the anti-arrhythmic loading.

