Medtronic Business Restricted

LINQ QT Study Clinical Investigation Plan						
21 SEP 2022	Version 2 Page 7 of 48			Medtronic		
	 Exclusion Criteria: Patients who have a contraindication to long-term antiarrhythmic therapy Patients not suitable for long-term antiarrhythmic therapy 					
	 Patients with a previo cardiac resynchroniza defibrillator (ICDs)) Co-enrollment in anoth during the course of the 	tion requir er study or p is clinical stu	ing > 40% pac blanning to partici	tion (i.e., cardi cing, implanta pate in a concu nfound the resu	ac pacemaker or ble cardioverter rrent device study lts	
Study Procedures and Assessments	Study Procedure	Baseline	Index Antiarrhythmic Loading Event	(Optional) 2, 4, 8 week	90-day Visit/Study Exit	
	Patient Informed Consent	Х				
	Inclusion/Exclusion Assessment	Х				
	Cardiovascular (CV) and Medical History	Х				
	Demographics	Х				
	Physical Exam	Х	Х	Х	X	
	Blood Labs	Х	Х	Х	X	
	CV Symptoms*optional	Х	Х	Х	X	
	Medications	Х	Х	Х	Х	
	12-Lead ECG	Х	Х	Х	Х	
	2D Echocardiogram*optional	Х				
	Holter/ VitalPatch [®] RTM		Х	Х	X	
	MyCareLink [®] Daily Manual Transmissions	Х	х	Х	X	
	Patient Activations		Х	Х	X	
Study exit X Serious, Cardiovascular- related Adverse Events X X					X	
		Х	X			
	Study deviations Report upon occurrence					
Safety Assessments	There are no defined safety end not to demonstrate safety or ef	ndpoints in the LINQ QT study as the purpose of the study is effectiveness. Cardiovascular-related (CV) adverse events that				

Medtronic Business Restricted

LINQ QT Stu	udy Clinical Investigation F	Plan			
21 SEP 2022	21 SEP 2022 Version 2 Page 8 of 48			Medtronic	
	result in hospitalization due to anti-arrhythmic loading will be collected throughout the duration of the subject's participation in the study, beginning after the initial in- hospital/out-patient anti-arrhythmic loading.				
Statistics	Since the study will be exploratory in nature and the study objectives are descriptive, no clinical endpoints will be developed. LINQ™/LINQII [™] derived data will be summarized using descriptive statistics.				

3. Introduction

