3.1 Background

The QT interval on the electrocardiogram (ECG) has gained clinical importance, primarily because prolongation of this interval can predispose to a potentially fatal ventricular arrhythmia known as torsades de pointes, which could in turn lead to sudden cardiac death [1]. Multiple factors have been implicated in causing QT prolongation and torsades de pointes. Among these, an important risk factor for long QT syndrome is the use of QT prolonging drugs. A QT interval greater than 500 milliseconds (ms) has been shown to correlate with higher risk of torsades de pointes.

There are several commonly used medications that could lengthen QT and cause QT prolongation. One such class of medications are antiarrhythmic drugs which are used to treat heart rhythm disorders. These drugs are frequently prescribed in everyday clinical practice for the management of atrial fibrillation (AF) that affects nearly 1–2% of the general population [2,3]. The commonly used antiarrhythmics for AF rhythm control management belong to Vaughan Williams' classes, Ic and III. Both these medication categories are well known to influence ventricular depolarization and repolarization, alter QT and corrected QT interval (QTc) intervals on surface ECG and affect to variable extents the left ventricular (LV) function [4–10].

There are several studies which have assessed the effect of antiarrhythmic drugs on QT interval prolongation. One such study [11] revealed significant QTmax and QTc interval prolongation following Sotalol (from 424 ± 40 ms to 460 ± 57 ms and from 446 ± 35 ms to 474 ± 48 ms, respectively, both p < 0.01) and Amiodarone (from 437 ± 41 ms to 504 ± 39 ms and from 469 ± 35 ms to 527 ± 50 ms, respectively, both p < 0.01). Another study [12] revealed a significant mortality benefit when dofetilide was used in patients with baseline QTc intervals less than 429 ms (risk ratio 0.3), while an increase in mortality was seen with dofetilide therapy in patients with baseline QTc intervals greater than 429 ms (risk ratio 1.3) [13].

Currently, there is no reliable way for continuous and long-term monitoring of QT intervals in patients undergoing antiarrhythmics drug loading. An implantable cardiac monitor which can continuously monitor QT intervals in patients taking QT prolonging drugs can enable clinicians to track day-to-day variability in the QT intervals and also study long-term QT trends in patients.

Medtronic Business Restricted

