4.1 Objectives

4.1.1 Primary Objective

The primary objective of the study is to determine if QT changes can be detected from LINQ[™] ECG that may occur during and after antiarrhythmic loading. The QT intervals before and after antiarrhythmic loading will be compared for all patients to analyze QT changes that may be caused due to antiarrhythmic drugs.

5. Study Design

The LINQ[™] QT Study is a prospective, non-randomized, multi-center, observational, post-market clinical study. The study is expected to be conducted at up to three study sites located in the United States and will enroll up to twenty study subjects. It is anticipated that if one study site cannot enroll at least 3 subjects per month, then additional study sites will be included to meet the total enrollment target of twenty subjects.

Study subjects implanted with LINQ[™]/LINQII[™] (no more than 50% patients implanted with LINQII[™]), but no greater than 2 years for LINQ[™] or 3 years for LINQII[™], or patients who are indicated to receive a LINQ[™]/LINQII[™] implant at least 7 days prior to antiarrhythmic drug loading will be considered for enrollment in this study.

Medtronic Business Restricted

LINO OT Study Clinica	I Investigation Dian		
		I	
21 SEP 2022	Version 2	Page 10 of 48	Medtronic

Figure 1: Study Flow Diagram

Medtronic Business Restricted

LINQ QT Study Clinical Investigation Plan			
21 SEP 2022	Version 2	Page 11 of 48	Medtronic

- I. Index Antiarrhythmic Loading Event
 - 1. Subjects with LINQ[™] Implants

2. Subjects with LINQII[™] Implants

II. Follow up period

Medtronic Business Restricted

LINQ QT Study Clinical Investigation Plan			
21 SEP 2022	Version 2	Page 12 of 48	Medtronic

- III. Follow up clinic visits
 - 1. Subjects with LINQ[™] Implants

2. Subjects with LINQII[™] Implants

Medtronic Business Restricted

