10.1 Definitions/Classifications

For the purposes of clinical report, event definitions align with the International Organization for Standardization standard 14155 (ISO 14155). Where the definition indicates "device", it refers to any device used in the study. This might be the device under investigation, or any market released component of the system. For the purposes of the clinical report, Medtronic will classify each adverse event according to ISO 14155:2020 definitions. The study will follow the definitions, however, is not claiming full compliance to ISO 14155:2020.

General			
Adverse Event (AE)	Untoward medical occurrence, unintended disease or injury, or untoward clinical signs (including abnormal laboratory findings) in subjects, users or other persons, whether or not related to the investigational medical device and whether anticipated or unanticipated NOTE 1: This definition includes events related to the investigational medical device or the comparator. NOTE 2: This definition includes events related to the procedures involved. NOTE 3: For users or other persons, this definition is restricted to events related to investigational medical devices.		
	(ISO 14155:2020, 3.2)		
Relatedness			

Table 3: Adverse Event Definitions

Medtronic Business Restricted

21 SEP 2022	Version 2	Page 31 of 48	Medtronic
Cardiovascular Related	An adverse event relating to the heart and the blood vessels or the circulation (e.g., atrial fibrillation, myocardial infarction, stroke, peripheral vascular disease, heart failure).		
	Seriousness		
Serious Adverse Event (SAE) (ISO 14155)	Seriousness Adverse event that led to any of the following a) death, b) serious deterioration in the health of the subject, users, or other persons as defined by one or more of the following: 1) a life-threatening illness or injury, or 2) a permanent impairment of a body structure or a body function including chronic diseases, or 3) in-patient or prolonged hospitalization, or 4) medical or surgical intervention to prevent life- threatening illness or injury, or permanent impairment to a body structure or a body function, c) foetal distress, foetal death, a congenital abnormality, or birth defect including physical or mental impairment Note 1: Planned hospitalization for a pre-existing condition, or a procedure required by the CIP, without serious deterioration in health, is not considered a serious adverse event. (ISO 14155:2020, 3.45)		

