10.2.1 Adverse Event Classification

AEs will be classified according to the standard definitions as outlined below:

Medtronic Business Restricted

21 SEP 2022 Version 2 Page 33 of 48

What is classified?	Who classifies?	Classification Parameters	
Relatedness	Investigator	CV Related, resulting from anti-	
		arrythmia loading	
		hospitalization	
	Sponsor	Resulting from anti-arrythmia	
		loading hospitalization	
Serious	Investigator	SAE	
	Sponsor	SAE	
	Investigator	Based on presenting signs and	
Diagnosis		symptoms and other	
		supporting data	
	Sponsor	MedDRA term assigned based	
		on the data provided by	
		Investigator	

Table 4 Adverse Event Classification Responsibilities

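### Adverse-event collection is worded to open only after the initial antiarrhythmic loading, so serious cardiovascular events with onset during loading get no adverse-event record

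*Protocol*

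**What the plan says.** The protocol states the start of adverse-event collection twice, in almost identical words. Section 10 says collection runs through the subject's participation, "beginning after the initial in-hospital/out-patient anti-arrhythmic loading". The Safety Assessments row of the synopsis says "beginning after the initial in- hospital/out-patient anti-arrhythmic loading".

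Section 10 also fixes what is in scope: "Cardiovascular-related or serious adverse events that result in a hospitalization due to anti-arrhythmic loading will be collected". It adds that a death is collected only if it led to a cardiovascular hospitalization related to the loading.

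Section 4.1.1 sets the period of interest for the measurements. The study looks for QT changes "that may occur during and after antiarrhythmic loading", together with a comparison of QT before and after loading.

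Section 10.2 sends serious cardiovascular events to the AE eCRF and gives no start date of its own. The serious adverse event definition in Table 3 includes "3) in-patient or prolonged hospitalization".

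**The concern.** The study observes patients while a QT-prolonging drug is being loaded. Section 3.1 gives the clinical reason: QT prolongation can lead to torsades de pointes and sudden cardiac death, and "A QT interval greater than 500 milliseconds (ms) has been shown to correlate with higher risk of torsades de pointes". The loading days are therefore days on which an event due to loading could arise. They are also days on which QT is being measured for the primary objective.

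A collection window that opens only once the initial loading is over leaves those days out. Two things are at stake. The listing of loading-related events would have a gap at loading itself. And a QT change seen during loading could not be read alongside adverse events from the same days, because no adverse-event record would exist for them.

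**Working it through.** No arithmetic applies. The protocol states no event rate and no safety endpoint, so the check is to apply the written rule to the cases that can arise.

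**Periods side by side**

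| Item | Place in the protocol | Period covered |
|---|---|---|
| QT measurement | 4.1.1, 11.2.1 | before, during and after loading |
| Study participation | 7.2 | from signed consent, which precedes loading |
| Event collection | Synopsis, Section 10 | after the initial loading, to exit |
| AE eCRF reporting | 10.2 | no start date given |

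The loading days fall in the first two rows and outside the third. Section 10 is also awkward within itself: it speaks of collection across the whole of participation and then starts it after loading, although participation began at consent.

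**The rule applied to four cases**

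1. *Out-patient loading, with an arrhythmia on a loading day that leads to admission.* The event results in a hospitalization due to loading, so its type is in scope. Its onset precedes the window. Not collected on a plain reading.
2. *In-hospital loading, with a life-threatening arrhythmia on a loading day.* The onset again precedes the window. In addition, the subject is already an inpatient, so the event prolongs a stay and does not bring one about. Table 3 counts prolongation as serious; the collection sentence in Section 10 does not mention it. Moving the start date alone would leave this case uncertain.
3. *Death during in-hospital loading.* The sentence on deaths requires a resulting cardiovascular hospitalization. The subject was already in hospital, so the death may not qualify. Section 8.12 would still record death as the reason for exit, but that is not an adverse-event record.
4. *Event after loading that leads to admission because of the loading.* Inside the window and in scope. Collected.

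Only the fourth case clearly yields an adverse-event record. Section 10.2 does not rescue the others: it says how reportable events are recorded and does not reopen a period that Section 10 has closed.

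**Who is affected.** Under Section 7.3 every subject must be scheduled for loading, and Section 11.3 allows up to 20 subjects. The rule therefore bears on the whole cohort.

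**The case against.** The strongest reply is that the narrow scope is deliberate. Section 5.2 says safety is not a primary focus: the study is observational, its data do not guide treatment, and the device's safety profile is known. The synopsis defines no safety endpoints, and Section 10 notes that only approved products are used. This stands as a reason for a light safety section. It does not explain why a protocol that chooses to collect events due to loading should leave out loading itself.

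The second reply is that some of the relevant text cannot be read. The body of Table 2 and the content of Section 8.7 are not shown, and the visit marks in the synopsis row for serious cardiovascular adverse events cannot be assigned to columns. If any of these calls for event recording at the index loading, the defect becomes a contradiction to reconcile. This also stands, and it limits how firmly the point can be put.

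Third, loading-period information is not lost altogether. The synopsis schedules a 12-lead ECG and Holter or patch monitoring at the index event, Section 6.1 says the device records detected arrhythmias, and the reporting duties to authorities and the IRB in Section 10.2.2 remain. These are not adverse-event records with the diagnosis, action and outcome that Section 10.2 asks for.

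A reader might infer more, and the document does not support it:

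- *The event count would be presented as the risk of loading.* No such estimate is planned. Section 11.2 commits the analysis to the primary objective, which is descriptive QT.
- *Missed events would escape the suspension review.* The trigger in Section 13.10.2.1 concerns adverse events associated with the system or product under investigation. The study product is the monitor, so a drug-induced arrhythmia would not plainly meet it even if collected.
- *Table 4 contradicts the window.* Its category is causal. An event after the window opens can still result from an earlier loading hospitalization.

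**Conclusion.** The point holds on the plain wording of the synopsis and Section 10: a serious cardiovascular event with onset during the index loading gets no adverse-event record. The event listing is incomplete for that period, and QT changes during loading cannot be paired with adverse events from the same days. The descriptive QT analysis and the sample size are not touched.

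In size, the rule covers all of the up to 20 subjects. How many events it would miss cannot be derived. It is tempting to turn the sotalol and amiodarone QT figures in Section 3.1 into an expected number of subjects above 500 ms. Those figures come from another study after drug treatment, the protocol gives no drug mix, and a long QT is something this study measures, not an uncollected event. Any assumed risk of a serious event during loading would come from outside the document.

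The conclusion assumes that *after* means after the loading has been given, and that the unseen parts of Table 2, Section 8.7 and the synopsis schedule do not provide otherwise. To say that such events are never captured in any form would go too far.

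**What to change.** Make these changes together:

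1. In the Safety Assessments row of the synopsis and in Section 10, change the start of collection to: *beginning at the start of the index antiarrhythmic loading*.
2. State in Section 10 that an event prolonging the loading stay counts as resulting in hospitalization, consistent with the serious adverse event definition in Table 3.
3. Align the sentence on deaths in Section 10 with the same window, so that a death during loading is not left out because the subject was already an inpatient.
4. Check the synopsis schedule row for serious cardiovascular adverse events, Table 2 and Section 8.7 against the new wording, and reconcile any difference.

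The cost is a wording amendment and a few more AE eCRF entries for at most 20 subjects who are already assessed at the index event. No visit or procedure is added. Note 1 to the definition in Table 3 excludes planned admissions without serious deterioration, so a routine scheduled loading stay should not itself become an event. The downside for the sponsor is an event count that may look somewhat less favourable.
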